APPENDIX C: LYRIC CRITERIA

Lugano Classification was developed based on treatment with cytotoxic agents⁸. Immunotherapeutic drugs, may produce antitumor effects by potentiating endogenous cancer-specific immune responses. The response patterns seen with such an approach may extend beyond the typical time course of responses seen with cytotoxic agents, and can manifest as clinical responses after initial increases in tumor burden or even the appearance of new lesions. Thus, the 2014 Lugano Classification may not provide an accurate assessment of response to immunotherapeutic agents. Provisional modification of the Lugano criteria (LYRIC Criteria) may be used to assess participants who meet progressive disease per Lugano Classification^{8,10}.

Complete Response	Partial Response	Progressive Disease
Same as Lugano	Same as Lugano	
As with Lugano with the following exceptions:
 
Indeterminate response (IR)
 
 IR1: ≥50% increase in SPD of up to 6 measurable lesions in first 12 weeks of therapy without clinical deterioration IR2: <50% increase in the overall SPD with 
 a. Appearance of a new lesion(s), or b. ≥50% increase in PPD of a lesion or set of lesions at any time during treatment IR(3): Increase in FDG uptake without a concomitant increase in lesion size or number 
Patients with IR should continue on therapy and have repeat imaging after an additional 12 weeks (or sooner if clinically indicated).
 
Progressive disease criteria in these patients will be met if:
 
 IR1: An additional increase in the target SPD of ≥ 10% between the first IR1 timepoint and the SPD being assessed; or an increase in ≥ 5mm in either dimension of at least one lesion for lesions ≤ 2cm and 10mm for lesions > 2cm. IR2: the new or growing lesion(s) should be added to the target lesions (total of no more than 6) and there is PD if the SPD if the newly defined set of target lesions has increased ≥50% from their nadir value (which may precede the IR time point). IR3: There is evidence of PD by an increase in lesion size or the development of new lesions.

Abbreviations: SPD, sum of the product of the diameters; PPD, product of the perpendicular diameters.

APPENDIX D: NYHA CARDIAC GRADING CRITERIA

Modified from Dolgin et al., 1994⁹⁰

New York Heart Association Classification of Heart Failure	
Class I	No symptoms. Ordinary physical activity such as walking and climbing stairs does not cause fatigue or dyspnea.
Class II	Symptoms with ordinary physical activity. Walking or climbing stairs rapidly, walking uphill, walking or stair climbing after meals, in cold weather, in wind or when under emotional stress causes undue fatigue or dyspnea.
Class III	Symptoms with less than ordinary physical activity. Walking one to two blocks on the level and climbing more than one flight of stairs in normal conditions causes undue fatigue or dyspnea.
Class IV	Symptoms at rest. Inability to carry on any physical activity without fatigue or dyspnea.

APPENDIX E: CONTRACEPTION GUIDELINES

Pembrolizumab may have adverse effects on a fetus in uterus. Furthermore, it is not known if pembrolizumab has transient adverse effects on the composition of sperm.

For this trial, male subjects will be considered to be of non-reproductive potential if they have azoospermia (whether due to having had a vasectomy or due to an underlying medical condition).

Female subjects will be considered of non-reproductive potential if they are either:

- (postmenopausal (defined as at least 12 months with no menses without an alternative medical cause; in women < 45 years of age a high follicle stimulating hormone (FSH) level in the postmenopausal range may be used to confirm a post-menopausal state in women not using hormonal contraception or hormonal replacement therapy. In the absence of 12 months of amenorrhea, a single FSH measurement is insufficient.); **OR**
- have had a hysterectomy and/or bilateral oophorectomy, bilateral salpingectomy or bilateral tubal ligation/occlusion, at least 6 weeks prior to screening; **OR**
- has a congenital or acquired condition that prevents childbearing.

Female and male subjects of reproductive potential must agree to avoid becoming pregnant or impregnating a partner, respectively, while receiving study drug and for 120 days after the last dose of study drug by complying with one of the following:

1. Practice abstinence[†] from heterosexual activity; **OR**
2. Use (or have their partner use) acceptable contraception during heterosexual activity.

Single method (one of the following is acceptable): Combination method (requires use of two of the following):

- | | |
|--|---|
| 
 ○ intrauterine device (IUD) ○ vasectomy of a female subject's male partner ○ contraceptive rod implanted into the skin | 
 ○ diaphragm with spermicide (cannot be used in conjunction with cervical cap/spermicide) ○ cervical cap with spermicide (nulliparous women only) ○ contraceptive sponge (nulliparous women only) ○ male condom or female condom (cannot be used together) ○ hormonal contraceptive: oral contraceptive pill (estrogen/progestin pill or progestin-only pill), contraceptive skin patch, vaginal contraceptive ring, or subcutaneous contraceptive injection |
|--|---|

[†]Abstinence (relative to heterosexual activity) can be used as the sole method of contraception if it is consistently employed as the subject's preferred and usual lifestyle and if considered acceptable by local regulatory agencies and ERCs/IRBs. Periodic abstinence (e.g., calendar, ovulation, sympto-thermal, post-ovulation methods, etc.) and withdrawal are not acceptable methods of contraception.

[#]If a contraceptive method listed above is restricted by local regulations/guidelines, then it does not qualify as an acceptable method of contraception for subjects participating at sites in this country/region.

Subjects should be informed that taking the study medication may involve unknown risks to the fetus (unborn baby) if pregnancy were to occur during the study. In order to participate in the study subjects of childbearing potential must adhere to the contraception requirement (described above) from the day of study medication initiation (or 14 days prior to the initiation of study medication for oral contraception) throughout the study period up to 120 days after the last dose of trial therapy. If there is any question that a subject of childbearing potential will not reliably comply with the requirements for contraception, that subject should not be entered into the study.

APPENDIX F: REGISTRATION COVERSHEET**COH IRB#: A Phase 1/2 Study of Pembrolizumab plus Pralatrexate for Treatment of Relapsed or Refractory Peripheral T-cell Lymphomas****Data Coordinating Center:**

City of Hope
[name]
[name]
[contact]

Email: [contact] (use #secure# in subject line)**Site Principal Investigator**

Name:
Address:
Phone:
Fax:
e-mail:

CRA/Study Coordinator:		Contact Number:	
Patient's Initials: (F M L):		Institution:	
Medical Record No:		Investigator/Treating Physician:	
Patient's DOB:		IRB approval valid until (date):	
Sex: _____ Male _____ Female		Date Informed Consent Signed:	
		Projected start date of treatment:	
Race		Ethnicity	
 Black		 Hispanic	
 Caucasian		 Non-Hispanic	
 Asian		 Other _____	
 American Indian		 Other _____	
 Native Hawaiian/Pacific Islander		 Other _____	
 Other _____		Method of Payment: _____	
		Codes:	
		01 Private	06 Military or Veterans Adm. sponsored
		02 Medicare	07 Self-pay (no insurance)
		03 Medicare & private ins.	08 No means of payment (no insurance)
		04 Medicaid	09 Unknown
		05 Medicaid & Medicare	

Reason for Screen Failure:**Reason for Failing to Initiate Protocol Therapy:**

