- Agreement to use effective methods of contraception for both women of childbearing potential and male patients during the study and through 6 months post-last dose of pralatrexate for women and 3 months post-last dose of pralatrexate for man, and 120 days post-last dose of pembrolizumab for both women and men.

Main Exclusion Criteria

- Patients with adult T-cell leukemia/lymphoma.

Prior Therapy and Concomitant Therapy

- Prior allogeneic hematopoietic stem cell transplantation within the last 5 years.
- Prior autologous hematopoietic stem cell transplant within the last 60 days.
- Patients who received prior therapy with an anti-PD-1, anti-PD-L1, or anti-PD-L2 agent without having had evidence of objective response.
- Patients who received prior therapy with pralatrexate without having had evidence of objective response.
- Investigational agent or anti-cancer monoclonal antibody (mAb) within 21 days prior to Day 1 of therapy or who has not recovered (i.e. ≤ 1 or at baseline) from adverse events due to agents administered more than 21 days earlier.
- Prior chemotherapy, targeted small molecule therapy, or radiation therapy within 14 days prior to Day 1 of therapy or who has not recovered (i.e. ≤ 1 or at baseline) from adverse events due to a previously administered agent. Note: Subjects with \leq Grade 2 neuropathy are an exception and may qualify for the study.
- Antineoplastic biologic therapy or major surgery within 21 days of the first dose of trial medication. If subjects received major surgery more than 21 days ago, they must have recovered adequately from the toxicity and/or complications from the intervention prior to starting therapy.
- Received live vaccine or live-attenuated vaccine within 30 days prior to Day 1 of protocol therapy. Administration of killed vaccines is allowed.
- Systemic steroid therapy or on any other form of immunosuppressive therapy within 7 days prior to the first dose of trial treatment.

Other Illnesses and Conditions

- Diagnosis of immunodeficiency.
- Has a known additional malignancy that is progressing or requires active treatment. Exceptions include basal cell carcinoma of the skin or squamous cell carcinoma of the skin that has undergone potentially curative therapy or in situ cervical cancer.

- Congestive heart failure Class III/IV according to the New York Heart Association (NYHA) Functional Classification.
- Known severe hypersensitivity reaction to pembrolizumab, pralatrexate, leucovorin or any excipients.

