3.0 ELIGIBILITY CRITERIA

Participant MRN (COH Only):	Participant Initials (F, M, L):
Institution:	

Participants must meet all of the following criteria on screening examination to be eligible to participate in the study:

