15. If not receiving anticoagulants: International Normalized Ratio (INR) OR Prothrombin (PT) $\leq 1.5 \times \text{ULN}$ If on anticoagulant therapy: PT must be within therapeutic range of intended use of anticoagulants	ULN: INR: PT:	Date:
16. If not receiving anticoagulants: Activated Partial Thromboplastin Time (aPTT) $\leq 1.5 \times \text{ULN}$ If on anticoagulant therapy: aPTT must be within therapeutic range of intended use of anticoagulants	ULN: aPTT:	Date:

Participant MRN (COH Only):	Participant Initials (F, M, L):
Institution:	

17. Female of childbearing potential: negative urine or serum pregnancy test within 72 hours prior to receiving the first dose of study medication. If the urine test is positive or cannot be confirmed as negative, a serum pregnancy test will be required
	Urine:	Serum:	Date:

Contraception

- 18. Woman of childbearing potential (WOCBP):** use two effective methods of contraception (hormonal or barrier method) or be surgically sterile, or abstain from heterosexual activity for the course of the study through 6 months post last dose of pralatrexate and 120 days post last dose of pembrolizumab. WOCBP defined as not being surgically sterilized or have not been free from menses for >1 year.
- Male:** use two effective methods of contraception (barrier method) or abstain from heterosexual activity with the first dose of study therapy through 3 months post last dose of pralatrexate and 120 days post last dose of pembrolizumab.

Refer to [Appendix E for Contraception Guidelines](#).

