4.2.2 Registration Process

Allow up to 24 hours for the DCC to review. To register a participant, the following procedure must be followed:

1. The study team should contact the DCC via email to provide notification regarding the pending registration and communicate desired timeline of the registration, especially if it must be completed promptly to meet the registration window.
2. The study team will email a **Complete Registration Packet** to the DCC, which consists of a copy of the following documents:
 - Registration Cover Sheet ([Appendix F](#))
 - Completed Eligibility Checklist (printed from Section 3.0 of the protocol) with required signature(s)
 - Signed informed consent
 - Signed HIPAA authorization form (if separate from informed consent)
 - Signed subject's Bill of Rights (California only)

3. In some cases, the DCC may request additional documentation prior to registration. Please refer to the Work Instruction – Reviewing Packets and Registering Subjects for more information. A copy of this work instruction can be provided by the DCC, upon request.
4. When all documents are received, the DCC will review and work with the study team to resolve any missing elements. Any missing documents may delay registration. A participant failing to meet all requirements will not be registered and the study team will be immediately notified.
5. The DCC will send a Confirmation of Registration Form, including the subject study number and cohort assignment to:
 - The study team: Site Lead Investigator, treating physician/sub-investigator, protocol nurse, CRC and pharmacy (as needed)
 - The COH Study PI and COH study team designees (including but not limited to study monitor(s) and statistician(s)).
6. Upon receipt of the Confirmation of Registration Form, COH study team will register the patient in OnCore. DCC will register non-COH patients in OnCore.

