5.1 Study Overview

This is a prospective, single-arm, multi-center, open-label phase 1/2 study of pembrolizumab (MK-3475) plus pralatrexate in subjects with relapsed or refractory peripheral T-cell lymphomas (PTCL) that have failed at least one prior line of therapy.

In the phase 1 portion, pembrolizumab will be administered at a constant dose of 200 mg IV and pralatrexate will be dose-escalated (range from 15-30 mg/m² IV). The phase 1 portion will use a modified rolling 6 design allowing 3 patients to be treated and evaluated for dose-limiting toxicity simultaneously, with up to 6 patients per dose level. An MTD and RP2D will be selected based on toxicity and tolerability data.

In the phase 2 portion, pembrolizumab will be administered at a dose of 200 mg IV and pralatrexate at the RP2D selected in the phase 1 portion following the same schedule. The phase 2 portion will use a Gehan two-stage design with advancement to the second stage based on ORR in the first stage.

In both phases, patients will receive up to 24 months of combined pembrolizumab and pralatrexate therapy. In both phases, Vitamin B12, Folic acid and Leucovorin will be administered as indicated in the study calendar and [Section 5.13](#).

Each cycle = 21 days. Maximum duration of protocol therapy is 24 months.

Folic acid and Vitamin B12 supplementation is standard of care for pralatrexate therapy.

Folic acid is given daily during the course of therapy. Vitamin B12 is given every 3 cycles.

¹ Disease staging is performed at screening and every 4 cycles until disease progression or off study. Disease staging will be by either PET/CT (preferred) or CT scan, but, if disease is FDG-avid, will be PET/CT at baseline, Cycle 4 and every 8 cycles thereafter. Refer to [Study calendar](#) and [Section 11.1](#) for details.

² Peripheral blood for correlative studies will be collected on C1D1, C2D1, C4D1, C5D1, and at EOT (refer to [Table 9.3.1](#) for additional details).

³ End of treatment visit.

⁴ Follow-up Phase for patients who have completed treatment without disease progression will include staging every 12 weeks for the first year and every 18 weeks thereafter, until disease progression or off study.

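### Appendix E gives women a 120-day contraception period after treatment, 61–64 days shorter than the 6 months after pralatrexate that inclusion criterion 18 and the synopsis require

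*Combined protocol and SAP*

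**What the plan says.** **The longer rule.** Section 3.1, inclusion criterion 18, asks women of childbearing potential to use contraception, be surgically sterile or abstain "through 6 months post last dose of pralatrexate and 120 days post last dose of pembrolizumab". For men the pralatrexate period is 3 months and the pembrolizumab period is again 120 days. The synopsis (main inclusion criteria) has the same split: "through 6 months post-last dose of pralatrexate for women and 3 months post-last dose of pralatrexate for man", plus 120 days after pembrolizumab for both sexes.

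**The shorter rule.** Appendix E addresses female and male subjects together and sets the period as "while receiving study drug and for 120 days after the last dose of study drug". Near its end it repeats the period as "throughout the study period up to 120 days after the last dose of trial therapy", in a sentence that makes compliance a condition of taking part. Its opening rationale speaks only of pembrolizumab. A later general warning refers to the study medication without naming a drug, and pralatrexate appears nowhere in the appendix.

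**How the two connect.** Inclusion criterion 18 ends by referring the reader to Appendix E, and Section 5.13.4 does the same. Exclusion criterion 23 in Section 3.2, and the matching synopsis item on plans to conceive or father children, also use 120 days from the end of trial treatment.

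**Standing.** Section 3.0 says: "Participants must meet all of the following criteria on screening examination to be eligible to participate in the study". Under Section 4.2.2 the signed checklist printed from that section is part of the registration packet.

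**The concern.** The protocol gives two different end dates for the same obligation in women, and the shorter one sits in the appendix to which sites are sent. The omitted period belongs to pralatrexate, which Section 6.1.2 describes as capable of harming a fetus and as embryotoxic and fetotoxic in animals.

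Timing adds to this. The eligibility checklist is completed at registration, but the post-treatment period begins only at the last dose, and Section 5.1 states: "Maximum duration of protocol therapy is 24 months". Someone who looks up the period at that stage and opens Appendix E would find 120 days for everyone. Followed literally, that ends a woman's contraception about two months before the date set by inclusion criterion 18. What is at stake is participant safety; no endpoint, sample size or analysis is touched.

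**Working it through.** The plan has no derived figure to reproduce. The check is calendar arithmetic on the stated periods.

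**Inputs**
- Appendix E: 120 days, both sexes.
- Inclusion criterion 18, women: 6 months from the last pralatrexate dose and 120 days from the last pembrolizumab dose. Both must be met, so the later date counts.
- Inclusion criterion 18, men: 3 months and 120 days, read the same way.
- Table 5.3: pembrolizumab on Day 1, pralatrexate on Days 1 and 8 of a 21-day cycle.
- Section 5.2 and the Section 10 calendar: windows of ±3 days on cycle length and on visits.
- Calendar months, taken over every start date from 2018 to 2025: 6 months is 181–184 days and 3 months is 89–92 days.

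**Formula.** Let P be the last pralatrexate date, M the last pembrolizumab date and S the 6-month length in days. Take the appendix's terms to cover both drugs.
- Appendix E ends at max(P, M) + 120.
- Inclusion criterion 18 (women) ends at max(P + S, M + 120).

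**Pralatrexate stops with or after pembrolizumab (P ≥ M).** This is the usual order, because Day 8 follows Day 1. The gap is S − 120:
- 181 − 120 = 61 days
- 184 − 120 = 64 days

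Other conventions for 6 months give similar results: 6 × 30 days gives 60, 26 weeks gives 62, and 6 × 30.44 days gives about 63.

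**Pembrolizumab continues alone, L days beyond the last pralatrexate dose.** The gap is max(0, S − 120 − L). At nominal timing, k further cycles give L = 21k − 7 after a last Day 8 dose, or L = 21k after a last Day 1 dose.

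| Further cycles k | Gap after last Day 8 dose (nominal days) | Gap after last Day 1 dose (nominal days) |
|---|---|---|
| 1 | 47–50 | 40–43 |
| 2 | 26–29 | 19–22 |
| 3 | 5–8 | 0–1 |
| 4 | 0 | 0 |

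These are nominal only. With cycles of 18–24 days and the Day 8 dose falling 4–10 days after Day 1:
- One further cycle: L runs from 18 − 10 = 8 to 24 − 4 = 20, so the gap is 61 − 20 = 41 to 64 − 8 = 56 days.
- Three further cycles: L runs from 54 − 10 = 44 to 72 − 4 = 68, so the gap is 0 to 64 − 44 = 20 days.
- Four further cycles: L can be as short as 72 − 10 = 62, leaving up to 64 − 62 = 2 days.

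Hence the gap closes after roughly three to four cycles, not at a fixed point.

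**Men.** 120 − 92 = 28 and 120 − 89 = 31, so Appendix E's 120 days exceeds the 3-month period by 28–31 days. There is no shortfall.

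**Alternative reading.** If the appendix's first statement means pembrolizumab only, the clock starts 7 days earlier in a regular last cycle. The gap is then 61 + 7 = 68 to 64 + 7 = 71 days.

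**The case against.** The strongest answer is that the longer rule already governs. Inclusion criterion 18 is specific by drug and sex, lies in the binding section, is repeated in the synopsis and is signed off at registration. A woman who follows it satisfies both texts. The appendix is titled as guidelines, and nothing in it waives the criterion. The sections on removal from therapy and follow-up (5.10 and 5.11) and the calendar notes do not send staff to Appendix E for a duration. Where criterion 18 does so, the 6-month rule stands just above the pointer. All of this stands and limits the severity. It does not make the appendix correct: its statements are worded as requirements and give the wrong period for women.

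A second answer is that the appendix means pembrolizumab only. Its rationale names only that drug, 120 days is the pembrolizumab period, and the protocol uses the term study drug loosely (for pembrolizumab in Table 5.13.3, in a pralatrexate rule in Section 6.4). On that reading the first statement is incomplete rather than contradictory. The second statement, tied to trial therapy, points the other way. Either way, the appendix omits the 6-month period.

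A reader might infer more than the documents support:
- **That the protocol as a whole requires only 120 days.** It does not; Section 3 binds.
- **That a quantifiable fetal risk follows.** Section 8.2.4 refers to the package insert and the documents give no washout data, so the risk in the extra two months cannot be sized.
- **That the pregnancy-test schedule makes matters worse.** The last scheduled test is at the 30-day safety visit whichever period applies, so its timing is not a consequence of this discrepancy.
- **That patients are told the wrong period.** The consent pages were not available, so this is unknown.

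**Conclusion.** The inconsistency is real and should be corrected. Appendix E is 61–64 days short for women whose pralatrexate stops with or after pembrolizumab. That figure assumes calendar months and that the appendix's terms include pralatrexate. The shortfall is smaller, and eventually nil, when pembrolizumab is continued alone. It does not apply to men.

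I rate it low to moderate for patient safety, because the binding criterion already carries the right period and an early stop would require a site to rely on the appendix instead. The number of women affected cannot be stated: the documents give no count of women of childbearing potential, and maximum accrual is 40 patients of both sexes (Section 12.2).

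**What to change.** In both places where Appendix E states 120 days, substitute the later of (a) 6 months for women, or 3 months for men, counted from the final pralatrexate dose and (b) 120 days counted from the final pembrolizumab dose. Name pralatrexate beside pembrolizumab in the appendix's opening rationale. In the same amendment, bring exclusion criterion 23 and its synopsis counterpart into line, since both carry the undifferentiated 120 days.

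The cost is a few phrases and one rationale sentence, with no effect on sample size, endpoints or analysis. The sponsor should check whether the consent form needs the same change.
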